8.1.2 Reactogenicity (Solicited AE)

Reactogenicity events are AEs that are common and known to occur following administration of this type of study vaccine. Study clinicians will follow and collect resolution information for any reactogenicity symptoms that are not resolved within 7 days.

Solicited AEs (i.e., reactogenicity) will be collected using memory aids and recorded on the appropriate source document from the time of each vaccination through 7 days post each vaccination (Days 1-8 for the first vaccination, and Days 29-36 for the second vaccination if applicable).

For this study, solicited AEs will be:

- Injection site Pain
- Injection site Erythema
- Injection site Edema/Induration
- Headache
- Diarrhea
- Fatigue
- Myalgia
- Arthralgia
- Nausea
- Fever
- Chills

8.1.3 Serious Adverse Events (SAEs)

An adverse event or suspected adverse reaction is considered serious if in the view of the investigator or the sponsor, it results in any of the following:

- Death,
- A life-threatening adverse event (see section [8.1.4](#))
- Inpatient hospitalization or prolongation of existing hospitalization
 - A hospitalization/admission that is pre-planned (i.e., elective or scheduled surgery/chemotherapy arranged prior to the start of the study), a planned hospitalization for pre-existing condition, or a procedure required by the protocol, without a serious deterioration in health, is not considered a serious adverse event.
 - A hospitalization/admission that is solely driven by non-medical reasons (e.g., hospitalization for patient or Participant convenience) is not considered a serious adverse event.
 - Emergency room visits or stays in observation units that do not result in admission to the hospital would not be considered a serious adverse event. The reason for seeking medical care should be evaluated for meeting one of the other serious criteria.
- Persistent or significant incapacity or substantial disruption of the ability to conduct normal life functions
- A congenital anomaly/birth defect
- Important medical events that may not result in death, be life-threatening, or require hospitalization may be considered a serious adverse drug experience when, based upon appropriate medical judgment, they may jeopardize the patient or Participant and may require medical or surgical intervention to prevent one of the outcomes listed in this definition.

8.1.4 Life-threatening

An adverse event or suspected adverse reaction is considered "life-threatening" if, in the view of either the investigator or sponsor, its occurrence places the patient or Participant at immediate risk of death. It does not include an adverse event or suspected adverse reaction that, had it occurred in a more severe form, might have caused death. (21CFR312.32)

8.1.5 Adverse Events of Special Interest (AESIs)

Adverse Events of Special Interest (AESIs) represent any events for which additional data (besides the standard AE data) are desired. These may be at the request of the regulatory agency, pharmaceutical partner or the Sponsor, and driven by a regulatory requirement, or known or potential risk from the product or class.

AESIs will include:

- Hypersensitivity reactions and other allergic reactions
- Hyperimmune responses
- Thrombocytopenia
- Myocarditis (inflammation of the heart muscle) or pericarditis (inflammation of the thin tissue surrounding the heart [the pericardium]). These will be based on the CDC case definition criteria[44] of these conditions.
- SAEs considered related to the vaccine

AESI will be reported to the Sponsor on the SAE form, following the timelines for SAE reporting.

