6.1.3.4 Day 57, Visit 4 (+/- 7 days)

- In-person visit
- Current health status will be reviewed and any changes since the last visit will be noted.
- Samples will be collected for immunology/correlative studies (see section [7.3](#)).
- Standard antibody testing to assess immune response
- Unsolicited AEs, and SAEs, that have occurred since the last contact will be collected.
- If a participant elects to have a second or third booster vaccination on protocol, the date of administration of this dose will be considered Day 1. The minimum timeframe between booster vaccination doses will be 28 days. Day 57, Day 180, and Day 360 timepoints, if not yet reached on the original booster vaccination on protocol will be timed according to the participant's last vaccination dose.

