8.3 Type and Duration of Follow-up of Participants after Adverse Events

All AEs will be assessed for severity and relationship to study intervention. Collection of all AEs from the participant, solicited and unsolicited, will occur during the period from study product administration on Day 1 through 28 days after the last vaccination. Adverse events that are serious need to be recorded after 28 days following the last vaccine, only if they are related to the study intervention.

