8.5 Reporting of Serious Adverse Events

Any AE that meets protocol-defined serious criteria or meets the definition of Adverse Event of Special Interest that require expedited reporting must be submitted immediately (within 24 hours of awareness) to OSRO Safety using the CCR SAE report form.

All SAE reporting must include the elements described in section [8.4](#)

SAE reports will be submitted to the Center for Cancer Research (CCR) at: [contact] and to the CCR PI and study coordinator. CCR SAE report form and instructions can be found at: <https://ccrod.cancer.gov/confluence/pages/viewpage.action?pageId=157942842>

Following the assessment of the SAE by OSRO, other supporting documentation of the event may be requested by the OSRO Safety and should be provided as soon as possible.

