8.9 Halting Rules

8.9.1 Study Halting Criteria

If any of the below occurs, the Protocol Chair will halt accrual to the trial to conduct a detailed safety review. Prior to resumption of the study, an expedited safety report will be sent to and reviewed by FDA if requested. All events also must be evaluated by the SMC.

- Any participant experiences laryngospasm, bronchospasm or anaphylaxis within 24 hours after administration of vaccine that is considered related to vaccine.
- Two (2) or more participants experience an allergic reaction such as generalized urticaria defined as occurring at three or more body parts within 72 hours after administration of vaccine that is considered related to vaccine.
- Any participant experiences suspected or confirmed myocarditis and/or pericarditis related to the study vaccine within 6 weeks of administration.
- Any serious adverse event deemed related to the vaccine will result in a halt to study accrual and an ad hoc meeting of the Safety Monitoring Committee (SMC). After a discussion of the event, the decision will be made as to whether to halt further accrual or lift the hold on accrual, based on the facts of the case and emerging evidence. Participants already on trial who successfully completed the first dose without incident will be allowed to receive the second dose of the vaccine, as per the mRNA-1273 vaccine's Emergency Use Authorization (EUA) granted in December 2020.

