8.10 Safety Oversight

8.10.1 Safety Monitoring Committee (SMC)

The SMC is an independent group of at least 3 experts that monitors participant safety and advises The Sponsor. SMC members will be separate and independent of study staff participating in this trial and should not have scientific, financial, or other conflicts of interest related to this trial. The SMC will consist of members with appropriate expertise to contribute to the interpretation of data from this trial. A quorum will consist of a simple majority.

Given the frequency and urgency to review data, the SMC will not need to meet unless halting rules are met.

SMC will meet to evaluate any adverse events associated with myocarditis or pericarditis within 1-2 weeks of reporting of the event.

Cumulative AE data will be provided to the SMC after all participants have completed Day 36.

The SMC will meet when trial halting criteria are met, or as requested by the sponsor or PI.

The SMC will have a final review meeting at the end of the study.

Procedures for SMC reviews/meetings will be defined in the SMC charter. The SMC will review applicable data, including, but not limited to, enrollment, demographics, dosing data, clinical laboratory data, and safety data, at scheduled timepoints during this trial as defined in the SMC charter. The SMC will review blinded aggregate data in the open session of the SMC meetings.

Additional data may be requested by the SMC, and interim statistical reports may be generated as deemed necessary and appropriate by the Sponsor. As an outcome of each review/meeting, the SMC will make a recommendation as to the advisability of proceeding with study product administration, and to continue, modify, or terminate this trial.

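### A single suspected myocarditis or pericarditis case halts accrual for 6 weeks after a dose, but collection of non-serious events stops at 28 days and the 24-hour reporting entry does not mention suspected cases

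*Combined protocol and SAP*

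**What the plan says.** **Halting rule (8.9.1).** One of the four criteria is: "Any participant experiences suspected or confirmed myocarditis and/or pericarditis related to the study vaccine within 6 weeks of administration". The Protocol Chair then halts accrual for a safety review.

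**Collection period (8.3).** Collection of all adverse events (AEs), solicited or not, "will occur during the period from study product administration on Day 1 through 28 days after the last vaccination". After that, only serious events related to the intervention need recording. Appendix F note f and Appendix G note h repeat the rule.

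**Later visits.** The booster Day 57 visit (6.1.3.4) says: "Unsolicited AEs, and SAEs, that have occurred since the last contact will be collected". The Day 180 and Day 360 booster visits, and the Day 209 and Day 394 vaccine-naïve visits, have the same instruction.

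**24-hour reporting (8.5).** The duty covers an AE that is serious or "meets the definition of Adverse Event of Special Interest that require expedited reporting must be submitted immediately (within 24 hours of awareness").

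**Adverse events of special interest, AESIs (8.1.5).** Myocarditis and pericarditis are listed by name, followed by: "These will be based on the CDC case definition criteria". The criteria are cited but not set out. AESIs follow the reporting timelines for serious events.

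**Seriousness (8.1.3).** "Emergency room visits or stays in observation units that do not result in admission to the hospital would not be considered a serious adverse event", but "The reason for seeking medical care should be evaluated for meeting one of the other serious criteria". One of those criteria is the important medical event, which rests on medical judgment.

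**Oversight (8.10.1).** "SMC will meet to evaluate any adverse events associated with myocarditis or pericarditis within 1-2 weeks of reporting of the event".

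**The concern.** The sponsor chose a very sensitive halting rule: one case, on suspicion, up to 6 weeks after a dose. The rule works only if the case reaches the Protocol Chair. The collection rule is shorter than the halting window, and the rapid-reporting entry is worded differently from the halting criterion. A site that follows the plan as written could therefore see a non-serious case that meets the halting criterion and have no clear duty to record it or to report it quickly. The trial has two sites, and accrual would continue until the case became known.

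**Working it through.** No sample size, power or error rate is involved. The check compares day counts and wording.

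**(a) Collection period against halting window**

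- Halting window: 6 × 7 = 42 days after a dose (8.9.1).
- Required collection of non-serious AEs: 28 days after the last dose (8.3).
- Not covered: 42 − 28 = 14 days, that is days 29 to 42; 14/42 = 33% of the window.

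On the study calendar, using nominal days and taking the dose shown as the last:

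| | Booster cohorts | Vaccine-naïve cohorts |
|---|---|---|
| Last dose | Day 1 | Day 29 |
| Required collection ends | 1 + 28 = Day 29 | 29 + 28 = Day 57 |
| Halting window ends | 1 + 42 = Day 43 | 29 + 42 = Day 71 |
| Days not covered | 30 to 43 | 58 to 71 |
| Next visit asking about AEs | Day 57 | Day 209 |
| Nominal wait until that visit | 57 − 43 = 14 to 57 − 30 = 27 days | 209 − 71 = 138 to 209 − 58 = 151 days |
| Scheduled troponin and ECG | Day 29 ± 14, latest Day 43 | Day 57 ± 14, latest Day 71 |
| Latest cardiac test after dose | 43 − 1 = 42 days | 71 − 29 = 42 days |

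The naïve Day 57 visit may take place up to 7 days late (Day 64), which would catch cases starting on Days 58 to 64. Later cases wait for Day 209. In both groups the protocol's own cardiac tests can fall on the last day of the halting window, 14 days after required collection of non-serious AEs has ended.

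**(b) Halting criteria against AESI entries**

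| Halting criterion (8.9.1) | AESI entry (8.1.5) | Tied to an outside definition? |
|---|---|---|
| Anaphylaxis, laryngospasm or bronchospasm | Hypersensitivity and other allergic reactions | No |
| Allergic reaction in two or more participants | Same | No |
| Suspected or confirmed myocarditis or pericarditis | Myocarditis or pericarditis, CDC criteria | Yes |
| Related serious event | Related serious event | No |

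One of four criteria depends on a source that the site cannot read in the protocol. A case falls into this gap only if it is suspected, judged related, still judged non-serious after the 8.1.3 evaluation, and not (or not yet) within the CDC criteria. Because the criteria are not reproduced, the share of such cases affected must be left as an assumption. It runs from near zero, if the criteria include a tier for suspected cases, to all of them, if they admit confirmed cases only.

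**The case against.** The strongest reply is that the plan already surrounds these cases with safeguards. Appendix E sends anyone with signs or symptoms in the weeks after vaccination to a cardiologist and stops further doses once an event is established. The team discusses each participant weekly (16.6.1). Committee review covers any event associated with these conditions, not only those meeting the CDC criteria. Suspected, vaccine-related cardiac inflammation is a natural candidate for the important-medical-event clause, which would make it serious. The halt itself does not depend on an 8.5 report. All of this stands, and it is why the practical effect is small. None of it requires a non-serious case in days 29 to 42 to be recorded, or sets a 24-hour deadline for a suspected one. The committee's 1-2 weeks run from reporting. Weekly meetings apply while participants are being actively treated. The 7-day site report in 16.4 depends on a policy that is not reproduced.

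It can also be said that 8.1.5 puts AESIs on the serious-event timelines, and that 8.5 has no end date. A case recognised as an AESI on day 35 would then be reportable. That is a fair reading, but those clauses set how fast to report. Section 8.3 and both calendar footnotes set how long to collect, and they make no exception for AESIs.

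A reader might infer more than the text supports:

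- *That a non-serious case is reported within 24 hours only if it satisfies the CDC definition.* The conditions are listed by name and are to be based on the criteria. That is looser than a strict test, and nothing tells a site to wait. An investigator could report a working diagnosis.
- *That a third of cases would be missed.* The 33% is a share of days, not of cases. Serious related cases are still recorded, and later visits may pick up the others.
- *That a missed halt or harm is likely.* The documents give no case frequency.

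**Conclusion.** The point holds in two parts of unequal strength. Part (a) rests on the trial's own text: for a non-serious case starting in days 29 to 42 after the final dose, required collection has ended while the halting criterion still applies. Later visits may find it, but in the vaccine-naïve cohorts possibly not until Day 209. This assumes that 8.3 governs how long AESIs are collected, as its wording and the footnotes suggest. Part (b) is a real difference in wording, but its size cannot be judged without the CDC criteria and may be near zero. Practical severity is low. No endpoint, estimate or halting threshold is affected. This is a cheap improvement to the alignment of a safety rule with the reporting that feeds it.

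**What to change.** 1. In 8.1.5, reword the entry to: *Suspected or confirmed myocarditis or pericarditis (cases classified using the CDC case definition criteria).* The 24-hour duty in 8.5 then applies to suspected cases without further change.
2. In 8.3, Appendix F note f and Appendix G note h, add: *Suspected or confirmed myocarditis or pericarditis is collected, and reported as an AESI within 24 hours of awareness, through 6 weeks after each vaccination, whatever its seriousness.* Counting from each vaccination also avoids having to know which dose will be the last when further boosters are optional.

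Leave 8.5, 8.9.1 and Appendix E as they are. A general sentence in 8.5 covering every halting criterion would be wider than needed, and would fit poorly with the allergic-reaction criterion, which requires two or more participants.

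The cost is wording, plus 14 more days of collection for one event type. No visit, sample or analysis changes. A few 24-hour reports will later be ruled out; the documents give no basis for estimating how many.

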8.2 Specification of Safety Parameters

8.2.1 Solicited Events

Solicited events are AEs that are common and known to occur following administration of study product.

8.2.2 Unsolicited Events

Unsolicited events are any other AEs that occur following administration of study

8.3 Type and Duration of Follow-up of Participants after Adverse Events

All AEs will be assessed for severity and relationship to study intervention. Collection of all AEs from the participant, solicited and unsolicited, will occur during the period from study product administration on Day 1 through 28 days after the last vaccination. Adverse events that are serious need to be recorded after 28 days following the last vaccine, only if they are related to the study intervention.

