4.6 Treatment Assignment

Participants from all four cohorts for Table 1 will be assigned to treatment arm 1. Enrollment for all cohorts will begin concurrently.

Table 1: Vaccine-Naïve Cohorts and Treatment Arm

| Cohort | Description | Arm | Sample Size | Intervention |
|--------|--|-----|-------------|--|
| 1 | Hematologic Low Immunosuppression | 1 | 20 | 100 µg (0.5 mL) mRNA-1273 injection on D1 and 29 |
| 2 | Hematologic Intermediate Immunosuppression | 1 | 20 | 100 µg (0.5 mL) mRNA-1273 injection on D1 and 29 |
| 3 | Hematologic High Immunosuppression | 1 | 20 | 100 µg (0.5 mL) mRNA-1273 injection on D1 and 29 |
| 4 | Solid Tumor on PD1/PDL1 Inhibitor* | 1 | Up to 20 | 100 µg (0.5 mL) mRNA-1273 injection on D1 and 29 |

*Solid tumor cohort is inclusive of all tumors for which PD1/PDL1 inhibitors are approved therapies, including Hodgkin Lymphoma or Primary Mediastinal B-Cell Lymphoma.

Participants from all seven cohorts in Table 2 will be assigned to treatment arm 2. Enrollment for all cohorts will begin concurrently.

Table 2: Booster Vaccine Cohorts and Treatment Arm

| Cohort | Description | Arm | Sample Size | Intervention |
|--------|---|-----|-------------|---|
| 5 | CLL Not On Active Therapy | 2 | 20 | 100 µg (0.5 mL) mRNA-1273 injection on D1 |
| 6 | CLL Receiving BTK* Inhibitor Interruption | 2 | 20 | 100 µg (0.5 mL) mRNA-1273 injection on D1 |
| 7 | CAR T Cell Therapy | 2 | 30 | 100 µg (0.5 mL) mRNA-1273 injection on D1 |
| 8 | Solid Tumor on PD1/PDL1 Inhibitor** | 2 | Up to 20 | 100 µg (0.5 mL) mRNA-1273 injection on D1 |
| 9 | Post-Allogeneic Transplant | 2 | Up to 20 | 100 µg (0.5 mL) mRNA-1273 injection on D1 |
| 10 | Other Hematologic Malignancy | 2 | Up to 20 | 100 µg (0.5 mL) mRNA-1273 injection on D1 |
| 11 | Other Adult Solid tumor | 2 | Up to 10 | 100 µg (0.5 mL) mRNA-1273 injection on D1 |

* This study will briefly interrupt BTKi therapy around the time of vaccination in a group of CLL participants in order to determine whether this approach improves vaccine response rates (discussed in detail in section 2.4.5). CLL participants that are currently receiving treatment with a BTKi therapy and are willing to hold their treatment around the time of vaccination will be eligible. In this group, BTKi therapy will be held for 1 week before vaccination until 2 weeks after vaccination (3 weeks total).

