6.1.3 Vaccine Administration and Follow-Up for Booster Vaccine Cohorts

Participants from the Vaccine-Naïve Cohorts who receive the additional booster will follow-up per the Booster Vaccine Cohort and will follow the below timeline. They will not be required to complete any Vaccine-Naïve Assessments after receiving the booster vaccine. They will become eligible for their respective booster per the Booster Vaccine Cohort 4 weeks after their second vaccination. A physical examination may be performed, as indicated, based on participant's recent clinical history, but for participants transitioning from the Vaccine-Naïve Cohorts, this will not be required. Similarly, baseline labs will not be required for Vaccine-Naïve participants who transition into the Booster Vaccine Cohorts.

Participants who enroll on trial after a previous booster vaccination off-trial will follow the same study calendar, as below, provided at least four weeks have passed from the last booster vaccination.

Similarly, participants who receive an initial booster vaccination from this protocol will be eligible for a second and a third booster vaccination and follow the study the same study calendar as below, provided at least four weeks have passed from the last booster vaccination. The date of

their second booster dose will be considered Day 1. If they receive a third booster dose on protocol, the calendar will be reset, and the date of their third booster will be considered Day 1.

6.1.3.1 Day 1, Visit 1, Booster Vaccine Dose 1

- Unless otherwise indicated, the following baseline evaluations can be performed within 28 days prior to vaccine administration. The screening evaluations and baseline evaluations may be performed on the same day. Any evaluations required at both timepoints will not need to be duplicated if this occurs. As noted above, participants who are transitioning from the Vaccine-Naïve cohorts will not need any baseline labs, as they are already enrolled on the protocol.
- Participants in the BTK inhibitor interruption arm must stop their BTK inhibitor therapy no later than Day -7 and may resume no sooner than Day 15.
- Eligibility baseline criteria for study entry and receipt of Dose 1 will be reviewed with the participant.
- Vital signs will be obtained, including weight, temperature, pulse, and blood pressure.
- Medical history will be reviewed to assure continued eligibility.

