8.1.1 Adverse Events (AEs)

ICH E6 defines an AE as any untoward medical occurrence in a participant or clinical investigation Participant administered a pharmaceutical product regardless of its causal relationship to the study treatment. FDA defines an AE as any untoward medical occurrence associated with the use of a drug in humans, whether or not considered drug related.

An AE can therefore be any unfavorable and unintended sign (including an abnormal laboratory finding), symptom, or disease temporally associated with the use of medicinal (investigational) product. The occurrence of an AE may come to the attention of study personnel during study visits and interviews of a study recipient presenting for medical care, or upon review by a study monitor.

All AEs, including solicited local (injection site) and systemic (subjective and quantitative) reactions, will be captured on the appropriate data collection form and eCRF. Information to be collected for AEs includes event description, date of onset, assessment of severity, relationship to study product and alternate etiology (assessed only by those with the training and authority to make a diagnosis and listed on the Form FDA 1572 as an investigator), date of resolution, seriousness and outcome. AEs occurring during the trial collection and reporting period will be documented appropriately regardless of relationship. AEs will be followed through resolution.

Any medical condition that is present at the time that the Participant is screened will be considered as baseline and not reported as an AE. However, if the severity of any pre-existing medical condition increases, it should be recorded as an AE.

If an event meets both the criteria of a study endpoint and an adverse event, the event will be reported either as a study endpoint or as an adverse event (not both).

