- d) Participants on the booster vaccine cohorts will receive an injection of mRNA-1273 into muscle on Day 1 and will be followed through 12 months post vaccination (Day 360). Participants will receive proof of vaccination.
- e) In-person clinical visits will occur at screening, and on Baseline/Days 1 (may occur on same day), 29, 57, 180 and at 360. These visits at clinic will take approximately 4-6 hours.
- f) Participants with CLL will have LDH and Beta-2 microglobulin drawn on Day 57. Participants in other cohorts will not have safety labs drawn at this visit.
- g) If a participant elects to have a second or third booster vaccination on protocol, the date of administration of the last dose will be considered Day 1. The minimum timeframe between booster vaccination doses will be 28 days. Day 57, Day 180, and Day 360 timepoints, if not yet reached on the original booster vaccination on protocol will be timed according to the participant's last vaccination dose.
- h) Collection of all AEs from the participant, solicited and unsolicited, will occur during the period from study product administration on Day 1 through 28 days after the last vaccination. Adverse events that are serious need to be recorded after 28 days following the last vaccine, only if they are related to the study intervention.
- i) The ECG may be performed up to 2 weeks before or 2 weeks after Day 29.

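### In Cohort 6, at least 7 of the 21 planned BTK inhibitor hold-days at the first on-study booster precede routine adverse event collection, a gap mainly in non-serious events

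*Combined protocol and SAP*

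**What the plan says.** **The hold.** The footnote to Table 2 in section 4.6 states: "This study will briefly interrupt BTKi therapy around the time of vaccination in a group of CLL participants". It sets the hold at one week before vaccination and two weeks after, three weeks in all. Section 6.1.3.1 gives the study days: these participants "must stop their BTK inhibitor therapy no later than Day -7 and may resume no sooner than Day 15".

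**The collection window.** Section 8.3 reads: "Collection of all AEs from the participant, solicited and unsolicited, will occur during the period from study product administration on Day 1". Appendix G footnote h repeats that collection "will occur during the period from study product administration on Day 1 through 28 days after the last vaccination". Section 8.2.2 defines unsolicited events as those following administration. No section gives Cohort 6 an earlier start.

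**The baseline rule.** Under section 8.1.1 a condition "present at the time that the Participant is screened will be considered as baseline and not reported as an AE". The same section then asks for an AE record when such a condition worsens.

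**Provisions that reach towards the hold week.**
- Section 7.1.3 includes a brief AE/SAE history immediately before vaccination.
- At the Day 1 visit in section 6.1.3.1, "Medical history will be reviewed to assure continued eligibility".
- Section 3.2 lists SAEs over the whole study as a primary safety endpoint.
- The Protocol Summary measures study duration from the start of screening.

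**The objective.** One primary safety objective in the Protocol Summary concerns booster doses in CLL participants who are off treatment or undergoing the three-week interruption. Section 3.2 does not repeat it.

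**The concern.** Stopping the drug is a study procedure. Participants begin it at least a week before the vaccine, yet the AE window is tied to the vaccine alone. A non-serious event that first appears in that week was not present at screening, so it is not baseline under section 8.1.1. It also precedes the window in section 8.3, so no rule assigns it a place.

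At stake is the safety description of a group named in a primary objective. A Cohort 6 safety table would carry no routine count for the first week of the interruption. Someone reading the table without section 8.3 could take that silence for an absence of events.

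There is a smaller related point. A person who stops the drug for a first study dose and is never injected belongs to none of the analysis sets in section 11.4.1, all of which require an injection, and may be replaced under section 6.3.3. The documents give no number for such participants, and it is probably small.

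**Working it through.** **Inputs**
- Hold length: 1 week before plus 2 weeks after vaccination (section 4.6).
- Stop by Day -7, resume from Day 15 (section 6.1.3.1). Day -7 is taken as the first held day and Day 14 as the last.
- AE window: from administration on Day 1 to 28 days after the last vaccination (section 8.3; Appendix G footnote h).
- Planned Cohort 6 size: 20 (section 4.6, Table 2).

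**Step 1: reproduce the plan's hold length.** 7 + 14 = 21 days, which matches the stated three weeks. By study day, Day -7 to Day -1 is 7 days and Day 1 to Day 14 is 14 days, again 21 with no Day 0. Exclusion criterion 5.2.2 uses the label Day 0 for screening. If Day 0 is a calendar day, the count is 8 + 14 = 22.

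**Step 2: compare with the window at the first on-study booster.**

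| Day count | Hold-days | Before window opens | Share | Covered |
|---|---|---|---|---|
| No Day 0 | 21 | 7 | 7/21 = 33.3% | 14 |
| Day 0 counted | 22 | 8 | 8/22 = 36.4% | 14 |

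These are minimum figures, because Day -7 is the latest permitted stop. Criterion 5.1.9 speaks of a hold of up to three weeks, so stops much earlier than that are not expected.

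**Step 3: cohort total.** 20 × 7 = 140 uncovered days out of 20 × 21 = 420. With Day 0: 20 × 8 = 160 out of 20 × 22 = 440.

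**Step 4: what other provisions recover.**
- *SAEs.* If the whole-study endpoint in section 3.2 starts at screening, as the study duration does, hold-week SAEs are included for those later injected. Section 8.5 (reporting within 24 hours of awareness) and section 4.9.2 (SAEs in screen-failure records) may catch others. Appendix C records all SAEs but yields to protocol text where they conflict.
- *Non-serious AEs.* Section 7.1.3 may bring them to light, but it names no look-back period and no rule for recording what is found. The Day 1 history review in section 6.1.3.1 is for eligibility.

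**Step 5: later holds.** If the next dose is given d days after the previous one, the hold week is days d - 7 to d - 1.
- If the window closes 28 days after the *most recent* dose: d = 28 (the minimum interval) puts the hold week at days 21 to 27, all covered; d = 36 puts it at days 29 to 35, all uncovered.
- If the window runs to 28 days after the participant's *final* study dose, every later hold lies inside it. The Appendix G calendar row uses the word final.

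**Step 6: effect of the change.** Opening collection at Day -7 raises coverage from 14 of 21 to 21 of 21 hold-days (from 14 of 22 to 22 of 22 with Day 0).

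**The case against.** The best defence is that the plan already asks the right question at the right time. Section 7.1.3 has staff take an AE/SAE history just before the injection, at the end of the hold week, and section 3.2 can be read to count SAEs from screening. On that view only minor events over one week are missing. Section 3.2 also ties solicited and unsolicited events to the period after each injection, so section 8.3 agrees with the endpoints. The objective concerns booster doses, and the interruption describes who receives them.

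Much of this stands. It limits the point to mainly non-serious events and makes the remedy easy. It does not supply a rule: a hold-week event found by the Day 1 history still predates the window in section 8.3.

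A reader might infer four stronger things that the documents do not support:
- *That all hold-week events, serious ones included, are lost.* Sections 3.2, 8.5 and 4.9.2 give routes for SAEs.
- *That every later hold is uncovered.* This requires reading the last vaccination as the most recent one; the calendar row points the other way.
- *That a third of the risk is unobserved.* The 33% is a share of days. Section 2.4.5 estimates that signaling returns after 7 days of holding, so on the plan's own reasoning the missing week comes largely before reactivation.
- *That collecting this week would test the claim in section 2.4.5 that holding does no harm.* That claim is argued from progression-free survival and long-term outcomes, which a week of AE data cannot address.

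**Conclusion.** The point holds for the first on-study booster in Cohort 6. At least 7 of 21 planned hold-days (33%), or 8 of 22 (36%) with a Day 0, have no routine AE collection: about 140 of 420 participant-days at full enrollment. This assumes 20 participants, a hold starting on Day -7 and section 8.3 applied as written. The loss is mainly of non-serious events. Whether SAEs are captured depends on where the study period is taken to begin. Later holds are probably covered, but the wording leaves doubt.

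This is a defect of ascertainment. The Safety Set remains right for post-injection rates. The study is descriptive with no hypothesis testing (section 11.1), and the hold is confined to clinically stable patients with at least six months of BTK inhibitor therapy (sections 2.4.5 and 5.1.9). The main results are not threatened; the change is worth making because it is cheap.

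**What to change.** For Cohort 6:
- Amend section 8.3 and Appendix G footnote h so that AEs and SAEs are recorded from a documented hold-start date.
- Use the pre-vaccination history in section 7.1.3 on Day 1 to ask about the whole hold week and record what is found.
- Tabulate events from hold start to injection separately from post-injection events. Keep Day 1 as the baseline for the latter, so that a condition begun during the hold counts again only if it worsens.
- Report the number who started the hold, the number injected, and any SAEs in those never injected. Fix a stopping point for that last group; 28 days from hold start would match the length of the plan's own window and cover the 21-day hold.
- State that the same rule applies to any later hold, which removes the ambiguity between last and final vaccination.

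The Safety Set, the immunogenicity sets, the replacement rule and the hold itself stay as they are.

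The cost is amended wording in two places, one extra case report form date, one extra table and about 7 more AE-collection days per participant (20 × 7 = 140 participant-days for one hold each). Injected participants need no extra visit; a participant never injected would need one contact.
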